- B. Headache attacks lasting 4-72 h (untreated or unsuccessfully treated) ^{Notes #2; #3}
- C. Headache has at least two of the following four characteristics:
 - unilateral location
 - pulsating quality
 - moderate or severe pain intensity
 - aggravation by or causing avoidance of routine physical activity (e.g., walking or climbing stairs)
- D. During headache at least one of the following:
 - nausea and/or vomiting
 - photophobia and phonophobia
- E. Not better accounted for by another ICHD-3 diagnosis.

Notes:

1. One or a few migraine attacks may be difficult to distinguish from symptomatic migraine-like attacks. Furthermore, the nature of a single or a few attacks may be difficult to understand. Therefore, at least five attacks are required. Individuals who otherwise meet criteria for 1.1 *Migraine without aura* but have had fewer than five attacks should be coded 1.5.1 *Probable migraine without aura*.
2. When the patient falls asleep during migraine and wakes up without it, duration of the attack is reckoned until the time of awakening.
3. In children and adolescents (aged under 18 years), attacks may last 2-72 hours (the evidence for untreated durations of less than two hours in children has not been substantiated).

Migraine With Aura

Previously used terms:

Classic or classical migraine; ophthalmic, hemiparaesthetic, hemiplegic or aphasic migraine; migraine accompagnée; complicated migraine.

Description:

Recurrent attacks, lasting minutes, of unilateral fully reversible visual, sensory or other CNS symptoms that usually develop gradually and are usually followed by headache and associated migraine symptoms.

Diagnostic criteria:

- A. At least two attacks fulfilling criteria B and C
- B. One or more of the following fully reversible aura symptoms:
 - visual
 - sensory
 - speech and/or language
 - motor
 - brainstem
 - retinal
- C. At least three of the following six characteristics:
 - at least one aura symptom spreads gradually over ≥ 5 minutes
 - two or more aura symptoms occur in succession
 - each individual aura symptom lasts 5-60 minutes ^{Note #1}
 - at least one aura symptom is unilateral ^{Note #2}
 - at least one aura symptom is positive ^{Note #3}
 - the aura is accompanied, or followed within 60 minutes, by headache
- D. Not better accounted for by another ICHD-3 diagnosis.

Notes:

1. When for example three symptoms occur during an aura, the acceptable maximal duration is 3×60 minutes. Motor symptoms may last up to 72 hours.

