10.2 Headache Diary – Preventive Therapies (Version 2.0)

Instructions: This form should be completed by the participant for each day the participant/subject experienced a headache/migraine.

1. Did you experience a headache today? Yes No
2. What time did your headache start? (24 hour clock) Woke up with this headache
3. What time did your headache end? (24 hour clock) Headache resolved after falling asleep
4. What acute pain medication(s), in addition to the study drug, did you take? (Choose all that apply)

 Acetaminophen	 Ibuprofen
 Almotriptan	 Naproxen
 Aspirin	 Naratriptan
 Dihydroergotamine (DHE)	 Rizatriptan
 Eletriptan	 Sumatriptan
 Ergotamine tartrate (ET)	 Zolmitriptan
 Frovatriptan	 Other, specify:
5. Describe the worst severity of your headache today? Complete one of the following pain severity scales:
 - a. Which word describes the severity of your headache?
 None Mild Moderate Severe Very Severe (for cluster headaches)
 - b. Rate your overall worst pain for this headache on a scale of 0-10: ("0" = no pain & "10" = the worst pain): 0 1 2 3 4 5 6 7 8 9 10
6. Do any of the following describe your pain? (Choose all that apply)

 Throbbing	 Pressure
 Pounding	 Pulsating with the heart beat
 Stabbing	 Squeezing
 Constant	 Other, specify:
 Sharp	
7. Where is the location of your headache pain? (Choose one)
 Right Left Bilateral (both sides)
8. Where is the location of your headache pain that hurts the most? (Choose all that apply)

 Top	 All over
 One Eye (specify,  left  right)	 Right Temple
 Around Eyes	 Left Temple
 Behind Eyes	 Front
 Back	 Other, specify:
 Neck	

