9. Does sound aggravate or make your headache worse? Yes No
10. Does light aggravate or make your headache worse? Yes No

11. Does routine physical activity (e.g. walking, climbing stairs) aggravate or make your headache worse? Yes No
12. Optional - Did you have any symptoms that came before and warned that this headache was going to start?
 Yes No Unknown
- a. If premonitory symptoms (symptoms that come *before* headache), which of the following did you experience? (Choose all that apply)
- | | |
|---|--|
|  Fatigue |  Yawning |
|  Difficulty concentrating |  Neck stiffness / pain |
|  Irritability |  Blurred vision |
|  Mood Changes |  Hypersensitivity to light |
|  Food Cravings |  Hypersensitivity to noise |
|  Nausea |  Other symptoms, specify: |
- b. If aura symptoms (neurological symptoms that come before or during headache), which type of aura did you have? (Choose all that apply)
- Visual aura (flashing lights, zig zag lines, dots, stars, sparkles, blind spots, shape and size distortion, temporary blindness, shimmering patches, tunnel vision, etc.)
 - Sensory aura (numbness, pins and needles)
 - Language/Speech aura (trouble understanding speech or producing it)
 - Motor aura (paralysis/muscle weakness of face, arm, or leg on one side)
 - Brainstem aura (double-vision, tinnitus or ringing in the ears, increased sense of hearing, unsteadiness when walking, slurred speech, vertigo or spinning sensation, or decreased level of alertness)
13. Did this headache reduce your ability to function? Yes No
- a. How would you describe your abilities to perform your usual daily activities at the onset of this headache?
- Able to work and function normally
 - Working ability or activity impaired to some degree
 - Working ability or activity severely impaired
 - Bed rest required
14. Did you receive acute headache treatment for your headache? Yes No
15. Complete one of the following questions:
- a. What time did this headache end? (24 hour clock)
- b. Headache ended after falling asleep? Yes No

Additional Pediatric-specific Elements

16. Did the headache change the participant's activity level (i.e., stop playing)? Yes No

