## 4. Definitions and Derivations

- 1) Baseline: Unless specified otherwise, baseline is defined as the non-missing value collected most recent to and before the time of the very first dose of the SM.
- 2) The 28-day rate for the prospective baseline = (total number of migraine days during the last 4 weeks prior to randomization/ total number of days prior to randomization) \*28.
- 3) Headache Day is any calendar day in which the subject experiences one of the following: a qualified migraine headache, a non-migraine headache that lasts continuously for more than 30 minutes, or a headache of any duration for which acute medication was used.
- 4) Severity of Headache is rated on a scale of 0-10: 0=None, 1- 3=Mild, 4-6=Moderate, 7-9=Severe, 10=Very severe.
- 5) Migraine is defined as any headache with or without aura that meets **both A and B**

**criteria** as described below (with matched question #s in 538P401 Protocol Appendix 2 Headache Diary).

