**A Criteria:**

At least **one** of the following:

- 1) Headache duration  $\geq 30$  minutes with pain medication(s):

*Questions #2 & #3: duration  $\geq 30$  min*

*Question #4 checked any of the boxes or Question #14 checked yes*

- 2) Headache duration  $\geq 60$  minutes with or without pain medication(s):

*Questions #2 & #3: duration  $\geq 60$  min*

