**B Criteria:**

At least **two** of the following:

- 1) Unilateral location:

*Question #7 checked with either Right or Left.*

- 2) Pulsatile quality:

*Question #6 checked with at least one of (throbbing, pounding, stabbing, constant, sharp, pressure, pulsating with the heartbeat, squeezing or other).*

- 3) At least moderate pain intensity:

*Question #5b rated  $\geq 4$  in the pain scale*

- 4) Aggravation by physical activity:

*Question #11 checked yes*

- 6) Headache/Migraine Duration is defined as the difference between the headache end date time minus start date time.
- 7) Change from Baseline = value at current time point – value at baseline.
- 8) Treatment Emergent Adverse Event (TEAE) = any adverse event with an onset date/time after first dose of study medication.
- 9) Duration of Adverse Event = AE end date – AE start date + 1
- 10) Duration of Treatment Exposure = date of last dose – date of first dose + 1
- 11) Percent of Study Medication Compliance is calculated as

$\% \text{ compliance} = 100 * (\text{Num}/\text{Den})$ , where

$$\text{Num} = \sum_{i=3}^7 \# \text{ of capsules dispensed at } \text{visit}_i - \# \text{ of capsules returned at } \text{visit}_{i+1}$$

$$\text{Den} = \sum_{i=3}^7 x_i \times (\# \text{ of days between } \text{visit}_i \text{ and } \text{visit}_{i+1}), \text{ where}$$

$x_i = \# \text{ of capsules per day assigned to be administered at } \text{visit}_i$

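### SAP Section 4 gives no duration rule for attacks the diary records as ended by sleep or present on waking; read literally, they cannot count as migraine days

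*SAP*

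**What the plan says.** **SAP Section 4, item 5.** The definition opens "Migraine is defined as any headache with or without aura that meets" and goes on to require both the A and the B criteria. Both routes through A are durations: at least 30 minutes with pain medication, or at least 60 minutes with or without it. Each is taken from the diary start and end items ("Questions #2 & #3: duration").

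**SAP Section 4, item 6.** "Headache/Migraine Duration is defined as the difference between the headache end date time minus start date time". No exception and no cross-reference follows.

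**Protocol Appendix 10.2 (diary).** Question 2 asks for the start time and carries an option for waking up with the headache. Question 3 reads "What time did your headache end? (24 hour clock) Headache resolved after falling asleep". Question 15 returns to the end of the headache under the instruction "Complete one of the following questions": either a clock time or a yes/no on whether it ended after falling asleep. No item asks when the child woke.

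**Protocol Appendix 10.1, Note 2 to the migraine-without-aura criteria.** "When the patient falls asleep during migraine and wakes up without it, duration of the attack is reckoned until the time of awakening". SAP Section 4 does not refer to this note.

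**SAP 5.1.** The 28-day rate is migraine days divided by days with a non-missing headache record, times 28. The same calculation is used for the prospective baseline.

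**The concern.** Nothing can replace the duration test in criterion A: not pain intensity, associated features or rescue use. An attack with no end or start time has no end-minus-start difference, so under the stated rule it cannot be shown to reach 30 or 60 minutes. Its day still has a headache record, so it appears to stay in the denominator and add nothing to the numerator. The loss would leave no trace in the diary-completeness figures.

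The derivation feeds the primary endpoint, its baseline covariate and the responder endpoint. It would also touch the randomization strata if the same algorithm supplies the baseline count. The headache-duration endpoint in SAP 5.2 sums durations, so these attacks would add no hours. If the gap is left open, whoever programs the endpoint must choose a rule, possibly after unblinding.

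**Working it through.** **1. The passages side by side**

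| Situation | Diary allows | SAP Section 4 needs | Rule in Section 4 |
|---|---|---|---|
| Attack ended by sleep | Sleep option at Question 3; at Question 15, sleep *instead of* an end time | End date-time | None |
| Attack present on waking | Woke-with-it option at Question 2; unclear whether it replaces or accompanies a time | Start date-time | None |

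Note 2 of Appendix 10.1 settles the end point of the first row in principle, but the diary collects no waking time with which to apply it. It does not address the second row.

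**2. One child.** Assume 28 complete diary days and 6 true migraine days, 2 of them without a computable duration.
- Days kept in the denominator: (4/28) × 28 = 4.0.
- Days treated as missing: (4/26) × 28 = 4.3.
- True value: 6.0.

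**3. The plan's own power figure.** Inputs from SAP 3.5: difference 1.1, SD 3, 117 per arm, two-sided 0.05.
- Standard error: 3 × √(2/117) = 0.392.
- Power: Φ(1.1/0.392 − 1.96) = Φ(0.84) = 80.1% (79.8% with the noncentral t).
- Dropout: 234/0.85 = 275.3, which gives 276 at 138 per arm.

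The plan's figures reproduce and are not in dispute.

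**4. Equal loss in both arms (illustration).** The documents give no share of attacks without a clock time, so f is an assumption. If a share f of true migraine days goes uncounted in every period and both arms, the difference becomes 1.1 × (1 − f). Two treatments of the SD bracket the result:
- SD held at 3.
- SD shrinking by independent thinning: SD² = (1 − f)² × 9 + f(1 − f)(b + q), where b and q are mean migraine days at baseline and on treatment. Assumed range: 4 and 2.5, up to 10 and 7.

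| f | Difference | Power, SD 3 | Power, SD shrinking |
|---|---|---|---|
| 0 | 1.10 | 80.1% | 80.1% |
| 5% | 1.045 | 75.9% | 76.3-78.6% |
| 10% | 0.99 | 71.4% | 72.2-77.0% |
| 20% | 0.88 | 61.2% | 63.7-73.3% |
| 30% | 0.77 | 50.1% | 55.0-68.8% |

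Example at f = 10%, SD 3: Φ(0.99/0.392 − 1.96) = Φ(0.56) = 71.4%.

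**5. Unequal loss.** Suppose both arms truly have m migraine days in the last 4 weeks, with shares f_A (SPN-538) and f_P (placebo) uncounted. The derived counts then differ by m(1 − f_P) − m(1 − f_A) = m(f_A − f_P). This is a false benefit if f_A is larger and a false disadvantage if f_P is larger. The documents give neither share, so the sign is open.

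**The case against.** **A rule may exist elsewhere.** SAP 6.7.1 on missing efficacy data is in the contents list, but its body is not in the text reviewed. A convention for missing attack times could sit there. This stands, and it is why the point is conditional. Even so, Section 4 is where duration is defined and it points nowhere else; Protocol 7.2 deals with missing 28-day values, not missing attack times.

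**The app may force a clock time.** Appendix 10.2 is a form, the instrument is an electronic application, and Protocol 6.1 says the timing of start and end is recorded. The printed layout does not show whether the woke-with-it option replaces a time. The instruction to complete one item governs Question 15, whereas criterion A reads Questions 2 and 3. All of this limits certainty. It does not remove the fact that the diary accepts sleep in place of an end time and the SAP is silent on it.

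**Note 2 already answers it.** For sleep-ended attacks it supplies a principle that the SAP does not contradict. It supplies neither a waking time nor anything for attacks present on waking.

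**Three stronger readings are tempting and not supported.**
- *The SAP discards these attacks.* No passage says that an incomputable duration means no migraine. That is the literal consequence of the rule, not a stated one.
- *The loss would favour SPN-538, because fatigue leads to more sleep-ended attacks.* Protocol Section 1 lists fatigue among frequent adverse events, but says that most events arose during titration and did not worsen in maintenance. The endpoint is the last 4 weeks of maintenance. Nothing links fatigue to sleep-ended attacks.
- *Migraines are also lost through the severity item.* Question 5 says "Complete one of the following pain severity scales", while the SAP criterion "At least moderate pain intensity" reads only the 0-10 scale (5b). Protocol 6.1 fixes severity on that scale, and B needs only two of four features. This is wording to reconcile, not a shown loss.

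**Conclusion.** The point holds as a gap in the derivation of the primary endpoint. As written, SAP Section 4 cannot classify an attack without a start or end time, and the diary permits such entries: firmly for sleep-ended attacks through Question 15, possibly for attacks present on waking. Unless SAP 6.7.1 or the app's design supplies the missing rule, migraine days are undercounted at baseline and on treatment, and the responder and headache-duration endpoints are affected too. Total headache days are less exposed, because a headache treated with acute medication counts whatever its duration.

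The size is unknown. An equal loss would shrink the treatment difference; the 71-77% power at a 10% loss rests on an assumed share, on no times being recovered, and on the planning t-test rather than the MMRM. An unequal loss could bias the comparison in either direction, and the documents do not show which.

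**What to change.** Before unblinding, amend SAP Section 4, items 5 and 6:

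1. For an attack ended by sleep (Question 3 option, or Question 15b answered yes), take the time of awakening as the end, following Appendix 10.1 Note 2.
2. For an attack present on waking, take the waking time as the start.
3. Where no waking time was captured, count criterion A as met if the B criteria are met.
4. State that these days stay in the denominator.
5. Add one sensitivity analysis that excludes days qualified only by this rule.

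If SAP 6.7.1 already holds a rule, cross-refer to it from item 6 and check it against these points. Separately, confirm that the app collects 5b, as Protocol 6.1 states, and reconcile the Appendix 10.2 instruction at Question 5.

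The cost is SAP wording, derivation code and one extra analysis, with an optional waking-time prompt in the app. Sample size and visits do not change. The downside is that step 3 waives the duration test where no time exists, so a few short sleep-ended headaches may count as migraine; the sensitivity analysis shows how much that matters.

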## 5. Study Variables

### 5.1. Primary Efficacy Variable

The primary efficacy endpoint of this study is the change in the monthly (28-day) rate of migraine days (MMDs) during the last 4 weeks of the 20-week double-blind Treatment Phase relative to the Prospective Baseline Period.

The 28-day rate of monthly migraine days (MMDs) days is calculated during the last 4 weeks of Doble-blind (DBL) period as

$$\frac{\# \text{ of days of migraine}}{\# \text{ of days with nonmissing headache record in the diary}} \times 28.$$

The 28-day rate of MMDs for the prospective baseline period is calculated as in above during the last 4 weeks of ‘prospective baseline’.

For MMRM analysis described in Section 7.1, the 28-day MMDs will be calculated for each visit window as depicted in the following Table.

Visit Window	Analysis Visit	Analysis Month
$2 \leq \text{Visit} \leq 3$	V3 (Prospective baseline)	Month 0
$\text{Visit } 3 < \text{to} \leq \text{Visit } 4$	V4 (Titration period 1)	Month 1
$\text{Visit } 4 < \text{to} \leq \text{Visit } 5$	V5 (Titration period 2)	Month 2
$\text{Visit } 5 < \text{to} \leq \text{Visit } 6$	V6 (Maintenance period 1)	Month 3
$\text{Visit } 6 < \text{to} \leq \text{Visit } 7$	V7 (Maintenance period 2)	Month 4
$\text{Visit } 7 < \text{to} \leq \text{Visit } 8$	V8 (Maintenance period 3)	Month 5

The 28-day MMDs will not be calculated after Visit 8. In other words, data from the Tapering period will not be included.

### 5.2. Secondary Efficacy Variables

The secondary efficacy endpoints are:

1. Responder, defined as a subject with  $\geq 50\%$  reduction in the MMDs during the last 4 weeks of the Treatment Phase relative to Prospective Baseline Period.
2. Change from baseline in the monthly migraine-specific acute rescue medication use in the last 4 weeks of the Treatment Phase.

The 28-day rate of migraine-specific acute rescue medication (MED) days is calculated during the last 4 weeks of DBL period as

$$\frac{\# \text{ of days rescue MED used}}{\# \text{ of days with nonmissing headache record in the diary}} \times 28$$

The 28-day rate for the prospective baseline is calculated as in above during the 4 weeks

of ‘prospective baseline’.

3. Change in the monthly rate of total headache days (migraine and non-migraine), duration and severity.
  - a) Total headache days: The 28-day rate of total headache days and prospective baseline are calculated using the same formula as for the primary endpoint.
  - b) Duration of headache: The 28-day duration is calculated during the last 4 weeks of DBL period as

$$\frac{\text{sum of all headache duration}}{\# \text{of days with nonmissing headache record in the diary}} \times 28$$

The 28-day rate for the prospective baseline is calculated as in above during the 4 weeks of ‘prospective baseline’.

- c) Severity of headache: The 28-day rate for severity will be calculated for each headache incidence of severity category (mild, moderate, severe, and very severe). The 28-day rate for mild severity is calculated during the last 4 weeks of DBL period as:

$$\frac{\# \text{of days with mild headache incidence}}{\# \text{of days with nonmissing headache record in the Diary}} \times 28$$

The 28-day rate for the prospective baseline is calculated as in above during the 4 weeks of ‘prospective baseline’.

The 28-day rates of moderate, severe, and very severe headache days will be calculated similarly.

4. Onset of treatment effect, defined as the time to first statistically significant treatment effect observed and maintained until the end of study in the primary endpoint.
5. Change from baseline in the Total Headache Disability Score as measured by PedMIDAS during the last 4 weeks of the Treatment Phase.
6. Change from baseline in the HRQoL as measured by the PedsQL 4.0 Total Scale Score during the last 4 weeks of the Treatment Phase for the self-report and the parent-report.

### 5.3. Safety Variables

The safety endpoints of this study include the following:

1. Incidence of AEs.
2. Clinical laboratory test results (blood chemistry and hematology, urinalysis).
3. Vital signs, physical and neurological examinations, eye exam and ECGs.
4. C-SSRS Assessment.
5. Cognitive Assessment.

## 6. Statistical Methods

### 6.1. General Principles

All statistical analysis, data processing, tabulation of descriptive statistics, calculation of inferential statistics, and graphical representations will be performed using SAS version 9.4 or higher.

All tabulations of analysis results will include summaries for the two treatments: SPN-538 and placebo.

Continuous variable summaries will include the number of subjects (n) with non-missing values, mean, standard deviation (SD), median, interquartile range (Q1 and Q3), minimum, and maximum.

Categorical variable summaries will include the frequency and percentage of subjects who are in the particular category or each possible value. In general, the denominator for the percentage calculation will be based upon the total number of subjects in the study population for the treatment groups, unless otherwise specified. The denominator for by-visit displays will be the number of subjects in the relevant study population with non-missing data at each study visit.

The minimum and maximum will be reported with the same degree of precision (i.e., the same number of decimal places) as the observed data. Measures of location (mean, Q1, Q3, and median) will be reported to 1 degree of precision more than the observed data and measures of spread (SD) will be reported to 2 degrees of precision more than the observed data.

Percentages will be presented to 1 decimal place, unless otherwise specified and with the following exceptions: a percentage of 0% will not be displayed (i.e., only the count of 0 will be displayed), and a percentage of 100% will be displayed with 0 decimal places.

Data collected at unscheduled time points will not be summarized but will be presented in subject listings.

Categorical variables will be analyzed using Pearson's chi-squared test or Fisher's exact test if 50% the expected cell counts <5.

Treatment comparison for all efficacy variables will be evaluated based on a two-sided significance level of 0.05.

All *P* values will be displayed in four decimals and rounded using standard scientific notation (e.g., 0.XXXX). If a *P* value less than 0.0001 occurs it will be shown in tables as <0.0001.

All collected data will be presented in listings.

